6.1.2.7 Occurrence and time to first occurrence of hypertension

Occurrence of an increase in blood pressure is a binary variable (Yes/No), defined as:

- systolic blood pressure (SBP) increase from BL ≥ 20 mmHg AND SBP ≥ 170 mmHg, or
- diastolic blood pressure (DBP) increase from BL ≥ 15 mmHg AND DBP ≥ 110 mmHg.

The date of occurrence of hypertension is defined as the first date where SBP criterion or DBP criterion is met, whichever occurs first.

At each visit, SBP and DBP are calculated as the average from the 3 readings.. If less than three readings are available, the non-missing readings will be used in the calculation of the average.

Baseline assessment is the assessment from Day 1. If this value is missing, then the latest available value from the screening period will be used.

Only events starting during the Safety Emergent Period (defined in Section [6.2](#)) will be taken into account.

The time to occurrence of hypertension for a subject with the event of interest will be calculated (in years) as:

$(\text{First event date} - \text{Analysis date of first dose intake} + 1) / 365.25$ Where ‘Analysis date of first dose intake’ is defined in Section 6.5.4 and where ‘First event date’ is the first date of occurrence of hypertension. The time to censoring for a subject without the event of interest is calculated as: $(\text{Date of last vital signs assessment during the Safety Emergent Period} - \text{Analysis date of first dose intake} + 1) / 365.25$ Refer to Sections 6.2 and 7.11.5 for more details regarding the Safety Emergent Period.

6.1.2.8 Rate of progression of CKD measured by annualized eGFR slope over time

Any eGFR values obtained from start of dialysis treatment (acute or chronic) will be excluded for the summaries and statistical analyses.

6.1.3 Additional Secondary Efficacy Endpoints

The additional secondary efficacy endpoints are listed in Table 5

Table 5 Additional Secondary Efficacy Endpoints

Number	Endpoint
	Hb correction and maintenance
1	Hb level averaged over weeks 28 to 36, 44 to 52, and 96 to 104 without use of rescue therapy within 6 weeks prior to and during this evaluation period.
2	Time to achieve the first Hb response as defined by primary endpoint.
3	Hb change from BL to each post-dosing time point.
4	Hb change from BL to the average Hb value of weeks 28 to 36, 44 to 52, and 96 to 104 regardless of the use of rescue therapy.
5	Proportion of Hb values within 10.0 to 12.0 g/dL and ≥ 10.0 g/dL in weeks 28 to 36, 44 to 52, and 96 to 104 without use of rescue therapy within 6 weeks prior to and during these 8-week evaluation periods.
	Hospitalizations
6	Occurrence (number) of hospitalizations, number of days of hospitalization per patient-year exposure and time to first hospitalization.
	Rescue Therapy Use
7	Time to first use of rescue therapy (composite of RBC transfusions, ESA use, and IV iron) in the first 24 weeks of treatment.
8	Occurrence and time to first use of RBC transfusions, number of RBC packs per month subject, volume of RBC transfused per month.
9	Occurrence and time to first use of ESA. Number of ESA-Weeks per year
10	Occurrence and time to first use of IV iron supplementation. Mean monthly IV iron (mg) per subject during day 1 to week 36, weeks 37-52 and weeks 53-104 (monthly defined as a period of 4 weeks).
	Change in Cholesterol Levels, Apolipoproteins
11	Change from BL to each post-dosing study visit in Total cholesterol, LDL/High-density Lipoprotein (HDL) ratio, Non-HDL cholesterol, Apolipoproteins A1 and B, ApoB/ApoA1 ratio.
12	Occurrence of mean LDL cholesterol <100 mg/dL calculated over weeks 12 to 28.
	Blood Pressure Effect
13	Occurrence of achieved antihypertensive treatment goal in CKD subjects (SBP < 130 mmHg and DBP < 80 mmHg) based on the mean SBP and mean DBP calculated over weeks 12 to 28.
Table continued on next page	

Number	Endpoint
	HRQoL
14	Change from BL to the average value of weeks 12 to 28 (SF-36 Physical Component Score (PCS), Anemia Subscale (“Additional Concerns”) of Functional Assessment of Cancer Therapy (FACT-An) Score, Total FACT-An Score, EQ-5D 5L VAS Score and Work Productivity and Activity Impairment (WPAI:ANS).
15	Patient Global Impression of Change (PGIC).
	Hepcidin, Iron status, HbA1c, and CKD progression
16	Changes from BL to each study visit (when measured) in Serum hepcidin, Serum ferritin, TSAT, HbA1c level, Fasting blood glucose, eGFR, Urine albumin/creatinine ratio, Time to (and proportion of subjects) Serum Creatinine having doubled during the study and Proportion of subjects with ESRD.

6.1.3.1 Hb level averaged over weeks 28 to 36, 44 to 52, and 96 to 104 without use of rescue therapy within 6 weeks prior to and during this evaluation period.

All scheduled and unscheduled hemoglobin values that belong to each period will be taken into account for calculating the average using the analysis windows (defined in [Table 31](#) Section [7.11.4](#)).

In addition, the averages over weeks 28-36, 44-52 and 96-104 will be categorized into the following categories:

- <10.0 g/dL,
- 10.0-12.0 g/dL,
- >12.0 g/dL,
- ≥ 10.0 g/dL.

In case a subject does not have any available Hb value within this evaluation period, or in case a subject requires rescue therapy within 6 weeks prior to and during this 8-week evaluation period, refer to Section [7.11.1](#) for imputation rules

6.1.3.2 Time to achieve the first Hb response as defined by primary endpoint.

6.1.3.2.1 Time (weeks) to achieve the first Hb response, without rescue therapy, as defined by the primary endpoint

Hb response is defined in Section [6.1.1.1](#)

For a subject without rescue therapy before Hb response, the time to achieve Hb response will be calculated (in weeks) as:

$$(\text{First event date} - \text{Analysis date of first dose intake} + 1) / 7$$

where ‘First event date’ is defined as ‘First date of both values that meet the criteria for response’ and ‘Analysis date of first dose intake’ is defined in Section [6.5.4](#)

For a subject without Hb response or with rescue therapy before Hb response, the time to censoring will be calculated (in weeks) as:

$$(\text{Min}[\text{Date of End of Efficacy Emergent Period}, \text{Date of initiation of rescue therapy}, \text{Analysis date of Week 24 visit}] - \text{Analysis date of first dose intake} + 1) / 7$$

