7.4 Analysis of Efficacy

7.4.1 Analysis of Primary Endpoint

There are 2 separate regionally based primary efficacy endpoints in this study depending upon whether the data are being filed to support submission to the EU EMA or to ex-EU health authorities, such as the US FDA.

EU (EMA)

The primary efficacy endpoint for EU (EMA) is a binary response endpoint (Hb response) defined as:

- Hb \geq 11.0 g/dL and a Hb increase from BL by \geq 1.0 g/dL in any subject with BL Hb $>$ 8.0 g/dL,
or
- an increase from BL by \geq 2.0 g/dL in any subject with BL Hb \leq 8.0 g/dL

at 2 consecutive visits separated by at least 5 days during the first 24 weeks of treatment without having received rescue therapy (i.e., RBC transfusion, ESA, or IV iron) prior to Hb response.

Subjects in FAS who either discontinue or receive rescue therapy before Hb response will be regarded as non-responders.

US (FDA)

The primary efficacy endpoint for US (FDA) is a quantitative endpoint defined as:

The change in Hb from BL to the average level during the evaluation period (defined as week 28 until week 52)

Hb results obtained from the central laboratory will be used for all efficacy analyses. Baseline Hb is defined as the mean of the 4 central laboratory Hb values prior to the first dose of study drug.

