6.1.1.1 Primary Efficacy Endpoint for EU (EMA)

The primary efficacy endpoint is a binary variable, Hb response (Yes/No), where Yes is defined as:

- Hb ≥ 11.0 g/dL and Hb increase from baseline by ≥ 1.0 g/dL, for subjects with baseline Hb > 8.0 g/dL; or
- Hb increase from baseline by ≥ 2.0 g/dL, for subjects with baseline Hb ≤ 8.0 g/dL

at two consecutive visits [dates] (with available data) separated at least 5 days during the first 24 weeks of treatment without having received rescue therapy (RBC transfusion, ESA, or IV iron) prior to Hb response.

Both scheduled and unscheduled Hb values from the central laboratory will be taken into account.

The first date of the two consecutive visits will be used as the date of response. Analysis visits will be used to define the week of response (see [Table 31](#), Section [7.11.4](#)).

Subjects who discontinued or received rescue therapy prior to the first Hb that fulfills the definition of response or before the second consecutive Hb value that fulfills the definition of response, will be classified as non-responders.

Baseline Hb is defined as the mean of four central laboratory Hb values: four latest Hb values prior or on the same date as first study drug intake (pre-dose).

Definition of rescue therapy is provided in Section [6.1.2.3](#)

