7.2.1 Disposition of Subjects

The following subject data will be summarized and presented:

- Number and percentage of subjects with informed consent, who discontinued before randomization and randomized (overall only);

- Number and percentage of subjects randomized in each analysis set, by treatment arm and overall;
- Number and percentage of subjects who completed and discontinued treatment in each period (primary treatment period and extended treatment period), by primary reason for treatment discontinuation and by treatment arm for All Randomized, SAF, FAS and PPS;
- Number and percentage of subjects who completed and discontinued the study, by primary reason for study discontinuation and by treatment arm for All Randomized and SAF;
- Number and percentage of subjects who completed and discontinued the post study follow-up period for All Randomized and SAF, and
- Number and percentage of subjects excluded from PPS by reason for exclusion defined in Section 5.3 by treatment arm for the FAS.

The following data will be presented graphically by treatment arm for the FAS and the SAF:

- Treatment discontinuation by reason using bar chart;
- Treatment discontinuation by time interval and reason using bar chart; and
- Time to treatment discontinuation using a Kaplan-Meier plot.

In addition, the following graphs will be done by treatment arm, for the FAS and PPS:

- Treatment discontinuation for lack of efficacy using a cumulative incidence plot;
- Treatment discontinuation for adverse event using a cumulative incidence plot.
- Treatment discontinuation for withdrawal by subject using a cumulative incidence plot.

Time intervals will be analyzed using the following categories:

- Less than 2 weeks
- At least 2 weeks, less than 4 weeks
- At least 4 weeks, less than 12 weeks
- At least 12 weeks, less than 24 weeks
- At least 24 weeks, less than 36 weeks
- At least 36 weeks, less than 52 weeks
- At least 52 weeks, less than 78 weeks
- 78 weeks or more
- Unknown.

In addition, the randomization stratification strata from both sources (CRF and IRT) will be reported by treatment arm. Discrepancy between stratification from CRF and IRT will be summarized and the total number of patients with discrepancy overall and for each stratification factor will be provided

Subjects who screened failure will also be listed.

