The cumulative incidence will be calculated as one minus the Kaplan-Meier estimate of the survival function. Two types of analyses can be performed: modeling the cause specific hazard or modeling the hazard of the sub-distribution. The first approach has been chosen in this SAP, because competing risks are assumed not to exist, since the main interest is to study the treatments effect and this method provides results to be generalized across datasets with different competing risks. One minus the Kaplan-Meier estimate can be interpreted as the probability that an event of interest occurs to a subject by time t, in the absence of any competing risk.

In addition to the cumulative incidence plot, the cumulative incidence at 3, 6 and 9 months with the 95% confidence interval will be reported using Greenwood's formula.

Model checking

The proportional hazards assumption will be checked graphically using a log-cumulative hazard plot against log-survival time. This plot will give approximately parallel lines if the proportional hazards assumption between treatment arms subgroups holds. This plot will be provided as part of the raw SAS outputs.

In addition, the number and percentage of subjects with an increase from baseline in blood pressure during the Safety Emergen Period will be reported by treatment arm (roxadustat and placebo) on the PPS. For subjects who have experienced more than one increase in blood pressure, only their first event following study treatment will be used in the analysis.

In addition, the incidence rate (per 100 subject years at risk) will be calculated as follows:

$$\frac{\text{Number of subjects with event}}{\text{Total cumulative time at risk (years)}} \times 100$$

Where Total cumulative time at risk is the sum of individual time at risk defined as either time to occurrence of the event or time to censoring for subjects with no event.

Number of subjects at risk is defined as the number of subjects with (censored or non-censored) times to the event of interest greater or equal to t.

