7.4.3 Analysis of Additional Secondary Efficacy Endpoints

All the analyses below will be superiority tests. These inferential analyses will be performed on the FAS and presented treatment effect as Roxadustat versus placebo.

Descriptive statistics will be presented by treatment arm.

7.4.3.1 Hb level averaged over weeks 28 to 36, 44 to 52, and 96 to 104 without use of rescue therapy within 6 weeks prior to and during these 8-week evaluation periods

Averaged Hb over weeks 28-36, 44 to 52 and 96 to 104 will be described by treatment arm on the FAS.

The SAS procedure will be similar to the one provided in Section 7.4.2.1

In addition, the number and proportion of subjects with average Hb over weeks 28-36 and over weeks 44-52 and 96-104 and by visit within the <10 g/dL, 10-12 g/dL and >12 g/dL categories will be reported.

7.4.3.2 Time to achieve the first Hb response as defined by primary endpoint for EU (EMA)

Time to achieve the first Hb response, without rescue therapy, will be analyzed using the same methods described in Section 7.4.2.7 on the FAS.

Superiority will be declared if the lower bound of the two-sided 95% confidence interval of the hazard ratio is above 1.

Cumulative incidence will be provided at 4, 8, 16, and 24 weeks with their associated 95% confidence interval reported using Greenwood's formula.

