7.11.6 End of Efficacy Emergent Period

For all subjects, the end of Efficacy Emergent Period will be defined as :

- **Minimum (Analysis date of Last Dose + 7 days , EOT Visit)**

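### Time to Hb response (SAP 6.1.3.2.1, 7.4.3.2): one minus Kaplan-Meier censors subjects whom the endpoint's own definition makes non-responders, so the Week 24 cumulative incidence is at or above the responder proportion in each arm

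*SAP*

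**What the plan says.** SAP 6.1.1.1 sets the rule for the EU primary endpoint. "Subjects who discontinued or received rescue therapy prior to the first Hb that fulfills the definition of response", or before the confirming second value, are classed as non-responders. Protocol 7.4.1 agrees: "Subjects in FAS who either discontinue or receive rescue therapy before Hb response will be regarded as non-responders".

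SAP 6.1.3.2.1 applies that response definition to a time-to-event endpoint but handles the same subjects differently: "For a subject without Hb response or with rescue therapy before Hb response, the time to censoring will be calculated (in weeks) as" the smallest of three dates. One is the "Date of initiation of rescue therapy". Another is the end of the Efficacy Emergent Period, given in 7.11.6 as "Minimum (Analysis date of Last Dose + 7 days , EOT Visit"), which is where a discontinued subject is cut off. The third is the Week 24 visit.

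SAP 7.4.3.2 sends the analysis to the methods of 7.4.2.7, on the FAS, and adds: "Cumulative incidence will be provided at 4, 8, 16, and 24 weeks with their associated 95% confidence interval". Section 7.4.2.7 computes cumulative incidence as one minus the Kaplan-Meier estimate. It names the cause-specific and sub-distribution approaches and explains its choice: "The first approach has been chosen in this SAP, because competing risks are assumed not to exist". It interprets the result as the event probability if no competing risk operated.

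**The concern.** The 7.4.2.7 text was written for hypertension. For Hb response, the endpoint's own definition contradicts the assumption of no competing risks: once a subject is rescued or stops treatment before response, no later Hb value can make that subject a responder. These are competing events. Censoring them lets Kaplan-Meier assume that they would have gone on to respond at the same rate as subjects still at risk.

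That assumption is also weak on clinical grounds. Protocol 5.1.5 ties ESA and IV iron rescue to insufficient Hb response, so the censoring is informative. SAP Appendix 7 (10.7) recognises this kind of problem. Inverse probability of censoring weighting is planned for rescue therapy, hospitalization, CKD progression and adverse events, but not for this endpoint.

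At stake is one reported figure. The study report could show two Week 24 response rates for one definition: the primary responder proportion, and a cumulative incidence that is equal to it or higher.

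**Working it through.** **Inputs.** From SAP Section 4: planning response rates of 65% (roxadustat) and 25% (placebo), 300 and 150 subjects, 5% two-sided. A two-proportion power calculation with these inputs gives over 99.99%, so the stated power of at least 95% is met and is not in question. The documents state no value for the Week 24 cumulative incidence, and no rate or timing for rescue or discontinuation before response. The exit fractions below are therefore assumptions.

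**What each estimator gives at Week 24.** Let r be the proportion who respond by Week 24 and c the proportion who exit first. Planned treatment is at least 52 weeks (SAP 3.2.3), so no administrative censoring falls before Week 24. The Aalen-Johansen estimate then equals r, the responder proportion. One minus Kaplan-Meier (1-KM) removes exits from the risk set and spreads their weight over those who remain. It can never be below r, and it exceeds r whenever a response follows a censored exit.

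**Size under proportional hazards.** The total cumulative hazard is −ln(1−r−c), and the response share of it is r/(r+c). Hence

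1-KM = 1 − (1−r−c)^(r/(r+c)).

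Roxadustat, r = 0.65, c = 0.05: 1 − 0.30^(0.65/0.70) = 0.673. Placebo, r = 0.25, c = 0.20: 1 − 0.55^(0.25/0.45) = 0.283.

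| Arm (true rate) | Assumed exits | 1-KM at Week 24 | Excess (points) |
|---|---|---|---|
| Roxadustat (65%) | 5% | 67.3% | 2.3 |
| | 10% | 69.9% | 4.9 |
| | 20% | 76.6% | 11.6 |
| Placebo (25%) | 10% | 26.5% | 1.5 |
| | 20% | 28.3% | 3.3 |
| | 30% | 30.4% | 5.4 |
| | 40% | 33.2% | 8.2 |

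**Effect of timing.** A simulation used visits at Weeks 1, 2 and every two weeks from 4 to 24, with 200,000 subjects per scenario. Times followed beta distributions scaled to 24 weeks. The ranges cover the exit fractions in the table above.

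| Timing of response / exit | Roxadustat excess | Placebo excess |
|---|---|---|
| Early, Beta(1.2,4) / late, Beta(3,1) | 0.3 to 1.4 | 0.2 to 0.7 |
| Early, Beta(1.2,4) / uniform | 1.3 to 6.0 | 0.8 to 3.7 |
| Uniform / uniform | 2.5 to 12.3 | 1.6 to 9.0 |
| Mid-period, Beta(2,2) / early, Beta(1,2) | 2.9 to 14.3 | 2.1 to 12.2 |

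In the first row the excess stays under 1 point except at 20% exits on roxadustat, where it is 1.4.

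**Between-arm difference.** The planned difference is 65 − 25 = 40 points. Under the proportional-hazards formula, 5% exits on roxadustat with 40% on placebo give 67.3 − 33.2 = 34.1. Exits of 20% and 10% give 76.6 − 26.5 = 50.1. The difference can shrink or grow.

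**The case against.** The strongest defence is that 7.4.2.7 discloses what it estimates. It names two approaches, chooses one with a reason, and gives the hypothetical interpretation. The title of 6.1.3.2.1 speaks of response without rescue therapy, which can be read the same way. This has some force: the estimator is coherent for a hypothetical quantity. It does not settle the matter, because the same title ties the endpoint to the primary definition, under which exits are failures.

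A second defence concerns size. Protocol 5.1.2 allows dose increases only from Week 4 and then every four weeks. Protocol 5.1.5 requires at least two increases before IV iron, and for ESA at least two increases or the maximum dose. Much of the rescue that follows the protocol should therefore start no earlier than about Week 8. Protocol 1.2.2.2 reports a phase 2 median time to response of 28 days at adequate starting doses. That pattern favours the smaller excesses, although transfusion and discontinuation can occur at any time. This stands, and it is why a range is shown.

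A third defence is that this is an additional secondary endpoint outside the hierarchy, and its superiority criterion rests on the hazard ratio rather than on the cumulative incidence. This also stands.

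Two stronger readings are tempting but unsupported. A reader might infer that the inflation is larger on placebo because rescue should be commoner there. The figures do not show it: at equal exits of 20%, the excess is 11.6 points on roxadustat and 3.3 on placebo. A reader might also extend the criticism to the by-reason plots in SAP 7.2.1, such as "Treatment discontinuation for lack of efficacy using a cumulative incidence plot", and infer that the curves would sum to more than total discontinuation. That section names no estimator, gives no rule for handling other reasons, and does not refer to 7.4.2.7.

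**Conclusion.** The point holds as a minor one. The inconsistency between 6.1.1.1 and 6.1.3.2.1 with 7.4.3.2 is in the text, and the direction within each arm is certain: the Week 24 cumulative incidence is at or above the responder proportion. The size is not known. It depends on exit fractions and timing that the documents do not give, and in the scenarios examined it runs from 0.2 to 14.3 points.

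A reader might infer that the plan favours roxadustat or undermines the primary result. Neither follows. The between-arm difference can move in either direction. The primary Cochran-Mantel-Haenszel comparison, its power and the fixed-sequence tests do not use this estimate. The Cox hazard ratio remains valid as a cause-specific hazard ratio.

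**What to change.** In SAP 7.4.3.2, replace the reference to one minus Kaplan-Meier with an Aalen-Johansen estimate at Weeks 4, 8, 16 and 24. Treat rescue, discontinuation and death before response as competing events, and use a confidence interval that matches the estimator. An equivalent choice is to keep these subjects at risk as non-responders to the end of the Week 24 window.

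Add a programming check that the value at the end of that window agrees with the FAS responder proportion in each arm. Keep the Cox model and describe its result as a cause-specific hazard ratio.

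The cost is a few lines of SAP text and a different estimator in the program. The event and exit dates are already derived under 6.1.3.2.1, so no new data are needed and no hypothesis test changes.

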6.1.3.3 Hb change from BL to each post-dosing time point

All scheduled and unscheduled hemoglobin values that belong to each window will be taken into account using one value per analysis window, as defined in [Table 31](#) and Section [7.11.4](#)

Baseline Hb is defined in Section [6.1.1.1](#)

At each visit, Hb will also be categorized into the following categories: <10 g/dL, 10-12 g/dL and >12 g/dL.

6.1.3.4 Hb change from BL to the average Hb value of weeks 28 to 36, 44 to 52, and 96 to 104 regardless of the use of rescue therapy

The same rules as defined in Section [6.1.2.1](#), but regardless use of rescue therapy.

